5.8.2 Procedures for discontinuation of a subject from investigational product

A subject that discontinues will always be asked about the reason(s) for discontinuation and the presence of any adverse events. The investigator(s) will perform the best possible observation(s), test(s) and evaluation(s) as well as give appropriate medication and all possible measures for the safety of the subject. They will also immediately inform AstraZeneca of the withdrawal. Adverse events will be followed up (See Sections 6.4.3 and 6.4.4); and study drug should be returned by the subject.

Subjects with an increased CK >10 x ULN will have their investigational product withheld and repeated CK test within 24 hours, but not exceeding 72 hours. If repeated CK is still >10 x ULN the subject should discontinue the investigational product. Otherwise investigational product may be resumed unless otherwise contraindicated.

Subjects with increased ALT and/ or ALT > 3 x ULN will have repeated liver function tests within 72 hours.

- **If the repeat ALT and AST are ≤ 3 x ULN**, the subject should be monitored according to the clinical study protocol
- **If the repeat ALT and/or AST are >3 x ULN but ≤ 8 x ULN and TB ≤ 1.5 x ULN**, medical history including details of risk factors for liver disease will be requested, see Appendix I. The Investigator will follow the subject every 72 hours until the ALT and AST are ≤ 2 x ULN or until ALT and AST are back to the baseline levels*. The frequency of retesting can decrease to once a week or less if abnormalities stabilize and the patient is asymptomatic. **If ALT and/or AST is >5 x ULN more than two weeks after initiation of close monitoring of ALT and AST**, the subject must be discontinued from study medication, the Sponsor notified and the end of treatment visit performed within 72 hours. At the end-of treatment visit, medical history including details of risk factors for liver disease will be requested and additional blood sampling done, see Appendix I.
- **If the repeat ALT and/or AST are >3 x ULN AND TB >1.5 x ULN at any time point**, the subject must be discontinued from study medication, the Sponsor notified and the end of treatment visit performed within 72 hours. At the end of treatment visit, medical history including details of risk factors for liver disease will be requested and additional blood sampling done, see Appendix I. The Investigator will follow the subject every 72 hours until the ALT and AST are ≤ 2 x ULN or until ALT and AST are back to the baseline levels*. The frequency of retesting can decrease to once a week or less if abnormalities stabilize and the patient is asymptomatic.
- **If the repeat ALT and/or AST >8 x ULN at any time point**, the subject must be discontinued from study medication, the Sponsor notified and the end of treatment visit performed within 72 hours. At the end of treatment visit, medical history including details of risk factors for liver disease will be requested and additional blood sampling done (if not already done), see Appendix I. The Investigator will follow the subject every 72 hours until the ALT and AST are ≤ 2 x ULN or until ALT and AST are back to the baseline levels*. The frequency of retesting can decrease to once a week or less if abnormalities stabilize and the patient is asymptomatic.

* unless there are specific reasons for the ALT and/or AST elevations e.g. liver cancer

Subjects who meet discontinuation criteria for lack of glycemic control at specified visits (See [Table 6](#)) will be scheduled for a repeated measurement within 3-5 days. If the repeated FPG value still meets the criteria for discontinuation, the subject should discontinue the investigational product. Otherwise investigational product may be resumed unless otherwise contraindicated.

Table 6 Discontinuation criteria for lack of glycemic control

Visit (Period C)	FPG
Weeks 4 and 6	> 240 mg/dL (13.3 mmol/L)
Week 8	> 220 mg/dL (12.3 mmol/L)
Week 10	> 200 mg/dL (11.2 mmol/L)

All randomised subjects who do not complete the treatment period (Period C) will complete the end of treatment visit (Week 12) study procedures as soon as possible but at the latest within 7 days after discontinuation of study drug. All randomised subjects will enter the 4-week follow-up period (Period D).

If a subject is withdrawn from study, see [Section 5.9](#).

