The subject will be asked to always self-monitor fasting blood glucose in case of symptoms suggestive of hypoglycaemia and to register any signs of hypoglycaemia in the supplied subject's card.

A hypoglycaemic event can be either

- An episode with symptoms and confirmed low glucose.
- An episode with low glucose.
- An episode with symptoms when glucose was not measured.

For the evaluation of hypoglycaemic events special attention will be given to as described below.

- Major hypoglycaemic events, defined as symptomatic events requiring external assistance due to severe impairment in consciousness or behaviour, with a capillary or plasma glucose value <3.0 mmol/L (<54 mg/dL), and prompt recovery after glucose or glucagons administration.

- Minor hypoglycaemic event, defined as either a symptomatic event with a capillary or plasma glucose value <3.5 mmol/L (<63 mg/dL), and no need for external assistance, or an asymptomatic blood glucose measurement <3.5 mmol/L (<63 mg/dL).
- Events suggestive for hypoglycaemia, with symptoms that the subject experiences as hypoglycaemia and no confirmative measurement.

Data to be collected for each hypoglycaemic event:

- Date of start and stop and time of the day for start
- If symptoms are present or not and which symptoms
- If finger stick value obtained and the plasma glucose value
- Intervention needed for recovery, max intensity, action taken, causality and possible contributing factors
- Time of last drug administration
- Time of last meal

The subject's card will be reviewed and data regarding hypoglycaemic events transcribed into the eCRFs at each clinical visit. A new subject's card for the next period will be handed over to the subject. If a major hypoglycaemic event occurs, or more than one minor event since last visit, the subject should contact the investigator. For recording of hypoglycaemic events/symptoms suggestive of hypoglycaemic events as AEs, see Section 6.4.3.

Hyperglycemic events

Fasting plasma glucose(FPG) will be measured at each visit. For the visits which pre-specified glycemic parameters on FPG are established (See Table 6), subjects are checked whether they have lack of glycemic control/hyperglycemic events.

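### Table 6 pairs mg/dL and mmol/L limits that do not agree at Weeks 8 and 10, and the protocol does not say which unit governs

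*Protocol*

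**What the plan says.** Table 6 in Protocol Section 5.8.2 gives one FPG limit per visit, in mg/dL with a mmol/L value in brackets:

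- Weeks 4 and 6: "> 240 mg/dL (13.3 mmol/L")
- Week 8: "> 220 mg/dL (12.3 mmol/L")
- Week 10: "> 200 mg/dL (11.2 mmol/L")

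A subject over the limit is remeasured within 3 to 5 days, and the rule then reads: "If the repeated FPG value still meets the criteria for discontinuation, the subject should discontinue the investigational product". Section 5.8.1, criterion 11, points to the same rule.

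Glucose is given in both units in one other place, the hypoglycaemia definitions of Section 6.4.9: "<3.0 mmol/L (<54 mg/dL") for major events and "<3.5 mmol/L (<63 mg/dL") for minor events.

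The remaining FPG limits, 240 mg/dL for withdrawal before randomisation and 180 mg/dL for performing the OGTT, appear in mg/dL only. Amendment 1, as shown, revises the liver criteria in Sections 5.8.1 and 5.8.2 and in Appendix I. It leaves Table 6 unchanged.

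**The concern.** A bracketed conversion normally restates the same limit. At Weeks 8 and 10 it does not: each mmol/L value lies above its mg/dL partner by more than one-decimal rounding can explain. Between the two values the row gives opposite answers, stop in mg/dL and continue in mmol/L.

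This matters more than a slip in background text because the table is a decision rule. By Section 5.4.1, FPG is the only central-laboratory glycaemic value released to investigators in Period C. A subject who stops has the Week 12 procedures brought forward to within 7 days and does not have the Week 12 OGTT or 24-hour urine collection. Two sites applying different units could therefore treat the same confirmed result differently.

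**Working it through.** **Inputs.** The three pairs in Table 6 are 240/13.3, 220/12.3 and 200/11.2. The two pairs in Section 6.4.9 are 54/3.0 and 63/3.5.

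**Step 1: the protocol's own factor.** 54 / 3.0 = 18.0 and 63 / 3.5 = 18.0 mg/dL per mmol/L.

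**Step 2: convert mg/dL to mmol/L (divide by 18.0, round to one decimal).**

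| Row | mg/dL | Calculated | Rounded | Printed |
|---|---|---|---|---|
| Weeks 4 and 6 | 240 | 13.33 | 13.3 | 13.3 (agrees) |
| Week 8 | 220 | 12.22 | 12.2 | 12.3 (differs) |
| Week 10 | 200 | 11.11 | 11.1 | 11.2 (differs) |

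A factor of 18.016 gives the same three rounded values.

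**Step 3: could another factor or rounding rule explain the table?** The factor that rounds to a printed value lies between mg/dL / (value + 0.05) and mg/dL / (value − 0.05):

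- 13.3 needs 17.98 to 18.11
- 12.3 needs 17.81 to 17.96
- 11.2 needs 17.78 to 17.94

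The first interval overlaps neither of the others, so no single factor gives all three rows. Multiplying by 0.056 gives 12.3 and 11.2 but turns the first row into 13.4. Always rounding up also makes the first row 13.4.

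**Step 4: convert back.** 12.3 × 18.0 = 221.4 mg/dL and 11.2 × 18.0 = 201.6 mg/dL. The bands of disagreement are 220 to 221.4 (1.4 mg/dL wide) and 200 to 201.6 (1.6 mg/dL wide). For results in whole mg/dL, the value that meets the mg/dL limit but not the mmol/L limit is 221 at Week 8 and 201 at Week 10. If the mmol/L result is itself rounded to one decimal before comparison, 222 (12.33, read as 12.3) and 202 (11.22, read as 11.2) are also affected. With 12.2 and 11.1 beside 220 and 200, and results so rounded, no whole-number value would be classified differently.

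**Step 5: how many subjects.** The protocol gives no FPG distribution, so this rests on assumptions: normal FPG with mean 150 to 160 and SD 35 to 40 mg/dL, and all 275 subjects still on treatment at Weeks 8 and 10.

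- Single values, ignoring the repeat: 0.64% to 0.95% fall in the Week 10 band and fewer in the Week 8 band.
- With the repeat, the two units give different decisions only when both measurements exceed the mg/dL limit and at least one does not exceed the mmol/L limit. With an assumed correlation of 0.6 to 0.9 between the two measurements, this gives about 1.0 to 3.0 subjects over both visits.
- With whole-number mg/dL results and an assumed within-subject SD of 10 to 20 mg/dL, it gives about 0.7 to 2.1 subjects.

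These counts compare every subject under one unit with every subject under the other. If all sites use mg/dL, no subject is affected.

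**The case against.** The strongest reply is that one unit governs in practice. Every other FPG limit is in mg/dL alone, and Table 6 prints mg/dL first. The natural reading is then a single limit with a mis-rounded bracket. That is the likely reading, but it is an inference. The protocol does not state it, and Section 6.4.9 prints mmol/L first.

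A second reply is that any one-decimal conversion leaves a sliver of disagreement. The Weeks 4 and 6 row has one too: 13.3 × 18.0 = 239.4, so an FPG of exactly 240 mg/dL (13.33) is above 13.3 but not above 240. This is correct, and a band alone does not prove an error. The evidence is that 12.3 and 11.2 are not the one-decimal roundings of 220 and 200, whereas 13.3 is that of 240.

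A third reply is the required repeat. A first value of 201 mg/dL at Week 10 followed by 190 means continue in either unit. This stands: one value in the band is not by itself an opposite decision, and the counts after confirmation are the ones to use.

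A reader might also infer that the mismatch disturbs the primary analysis, because stopping affects which HbA1c is used. The documents do not support that. A subject who stops still has the Week 12 procedures, including HbA1c, within 7 days. On nominal visit days and ignoring laboratory turnaround, a Week 10 stop puts that draw at about day 73 to 82 (70 + 3 to 5 + 0 to 7), against day 84. A Week 8 stop puts it at about day 59 to 68 (56 + 3 to 5 + 0 to 7). For so few of 275 subjects, no material effect is shown or expected. The sample size does not use these limits.

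**Conclusion.** The point holds as a conversion mismatch in two of the three rows of a treatment-stopping table, with no stated governing unit. The arithmetic needs nothing outside the protocol. The mismatch is 0.1 mmol/L per row, or 1.4 and 1.6 mg/dL.

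Its practical weight is very small: at most a few subjects classified differently, on an assumed FPG mean, SD and agreement between the two measurements, and none if every site reads mg/dL. It is a minor correction.

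It would go too far to say that the trial has two competing stopping rules, or that the mg/dL figures are right and the bracketed ones wrong. The documents show only that the paired values cannot both state the same limit.

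**What to change.** The sponsor should reconcile the mg/dL and mmol/L values in the Week 8 and Week 10 rows of Table 6 and add a line saying which unit governs. Which limit is intended is for the sponsor to determine. The cost is a few figures and one sentence in the next amendment, with no change to the sample size or the analysis.

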5.9 Withdrawal from study

Subjects are at any time free to withdraw from study (investigational product and assessments), without prejudice to further treatment (withdrawal of consent). Such subjects will always be asked about the reason(s) and the presence of any adverse events. If possible, they will be seen and assessed by an investigator. Adverse events will be followed up (See [Sections 6.4.3](#) and [6.4.4](#)); and study drug should be returned by the subject.

6. COLLECTION OF STUDY VARIABLES

6.1 Recording of data

Data will be entered in the Web Based Data Capture (WBDC) system at the study site. Trained study personnel will be responsible for entering data on the observations, tests and assessments specified in the protocol into the WBDC system and according to the electronic Case Report Form (eCRF Instructions).

The eCRF Instructions will also guide the study site in performing data entry. Data entered in the WBDC system will be immediately saved to a central database and changes tracked to provide an audit trail. Site personnel will enter the data in the eCRFs. The data will then be Source Data Verified (SDV), reviewed/ queried and updated as needed. The principal investigator will then sign the eCRF electronically.

When all data have been declared clean and signed by the investigator, the data will be frozen and then locked to prevent further editing. A copy of the eCRF will be archived at the study site when the study has been locked.

Dictionary coding

Medical coding is done using the most current version of MedDRA and the Bristol-Myers Squibb Drug Dictionary.

Management of external data

Data Management determines the format of the data to be received from external vendors and coordinates the flow of data to an external environment or clinical database (if applicable). Data Management will ensure that the data collection tool will be tested / validated as needed. External data reconciliation will be done with the clinical database as applicable.

The investigator(s) will record data on the observations, tests and assessments specified in the protocol on the electronic CRFs provided by AstraZeneca. The CRF will be accompanied with 'Instructions for the Investigator', which should be followed. These instructions provide guidance for the recording of study data in the CRF including how to change data incorrectly recorded.

6.2 Data collection and enrolment

6.2.1 Enrolment visit

Subjects will be screened for study participation (see [Table 1](#)) and eligibility will be determined by assessment of inclusion and exclusion criteria. The following assessments will be performed at the enrolment visit.

- Written informed consent
- Inclusion and exclusion criteria listed in Sections [4.1](#) and [4.2](#).
- Date of birth, sex, race
- Medical history and perform a complete physical examination (See Section [6.4.6](#)).
- Height, body weight, waist circumference, BMI, vital signs (sitting blood pressure and sitting heart rate) (see Section [6.4.8](#))
- HbA1c, FPG, fasting insulin, C-peptide
- Hepatitis screen panel, TSH, PT and APTT
- Standard Safety Laboratory Panel (Blood and Urine) (See Section [6.4.5](#))
- Spot urine sample (See Section [6.4.9](#))

- Urine HCG (Human chorionic gonadotropin) pregnancy test for women of child bearing potential (WOCBP)

6.2.2 Wash-out period (Period A)

The following assessments will be performed at Period A.

- FPG (Week -10 and -6)

6.2.3 Lead-in period (Period B)

The following assessment will be performed at Period B.

- Complete physical examination (Week -4)
- Vital signs, body weight (Week -4)
- ECG (See Section [6.4.7](#)) (Week -4)
- Urine HCG pregnancy test for WOCBP (Week -4)
- Standard Safety Laboratory Panel (Blood and Urine) (Week -4)
- HbA1c (Week -1)
- FPG (Week -4 and -1)

6.2.4 Treatment period (Period C)

The following assessment will be performed at Period C.

- Inclusion and exclusion criteria (Week 0)
- Brief/Complete physical examination
- Vital signs, body weight
- Orthostatic blood pressure and orthostatic heart rate (Week 0, 2, 4 and 12)
- Waist circumference (Week 0 and 12)
- ECG (Week 0 and 12)
- Urine HCG pregnancy test for WOCBP (Week 0, 1, 6 and 12)
- Standard Safety Laboratory Panel (Blood and Urine)
- Post-prandial glucose, insulin, C-peptide during OGTT (Week 0 and 12, if applicable) (See Section [6.3.1.2](#))

- Urine glucose, creatinine and sodium concentrations during OGTT (Week 0 and 12, if applicable) (See Section 6.3.1.2)
- PK sample collection (Week 1, 6, 10 and 12)
- Spot urine sample (See Section 6.4.9) (Week 0, 6 and 12)
- Serum sample for markers of bone metabolism (Week 0, 8 and 12)
- 24 hour urine collection (Week 0 and 12) (See Section 6.4.5)
- HbA1c, FPG, fasting insulin, fasting C-peptide, fasting serum lipids (See Section Table 7)
- Cystatine C (Week 0 and Week 12)

6.2.5 Follow-up procedures (Period D)

Subjects meeting one of the following criteria will participate in the Follow-Up Phase. Visit during this phase is scheduled to occur at Week 16.

- (a) Subjects completing Period C (Week 12)
- (b) Subject who discontinues double-blind study medication prior to Week 12 (will enter Period D after the last dose of study medication is administered)

The following assessment will be performed at Week 16.

- Brief physical examination
- Vital signs, body weight
- Orthostatic blood pressure
- Standard Safety Laboratory (Blood and Urine)
- HbA1c, FPG
- Spot urine sample
- Serum sample for markers of bone metabolism
- Cystatine C

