In Period B, Single-blind placebo will be used to assess subject's compliance with treatment. Subjects must demonstrate good compliance with investigational products ($\geq 80\%$ and $\leq 120\%$) during Period B, and have HbA1c $\geq 7\%$ but $\leq 10\%$ at Visit 5 (1 week before randomisation) to be eligible for entry into Period C. Subjects will be withdrawn from the study if they do not meet these criteria, and must return all unused investigational products. The Investigators will assess adverse event and provide medical therapy that is clinically needed for the subject.

Double-blind, Placebo-controlled, Treatment Phase - Period C (12 weeks; Visit 6-13)

Eligible subjects will participate in a randomized, double-blind, placebo-controlled treatment phase (Period C). Subjects will be randomized to one of five treatment arms that include dapagliflozin 1 mg, 2.5 mg, 5 mg, 10 mg or placebo in a 1:1:1:1:1 ratio. Subjects will be followed for a total of 12 weeks on double-blind study medication, returning for a visit one week after start of treatment, and then approximately every 2 weeks for evaluation of safety and efficacy. Once a patient is randomised, all visits should be scheduled relative to Visit 6. Any slippage in time from one visit must not accumulate to affect other visits. Period C must be at least 81 days and at the most 87 days (12 weeks \pm 3 days). Subject should not take investigational products prior to study visit at Visit 7, 10 and 12 (Week 1, 6 and 10). Investigational products should be taken soon after completing the study visit examinations.

All randomised Subjects who do not complete Period C will complete Visit 13 (Week 12) study procedures as soon as possible but at the latest within 7 days after discontinuation of investigational products.

Visit 6 (Week 0):

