Fasting blood sample (for HbA1c, FPG, fasting insulin, C-peptide, fasting serum lipids, standard safety laboratory panel, markers of bone metabolism, and cystatine C), and urine sample (for standard safety laboratory panel and spot urine, and 24 hour urine for subjects who give consent) will be obtained. At Visit 13(Week 12), 24 hour urine is not performed in subjects who did not complete Period C. OGTT will be performed except for subjects who did not perform OGTT at Week 0, discontinued or whose FPG \geq 180 mg/dl at Visit 12 (Week 10). PK samples are obtained at 60, 90, 120, 180 and 240 minutes after administration of investigational products. If OGTT is performed, the PK samples are obtained simultaneously with OGTT blood samples.

The investigators will assess adverse events, review concomitant medications, review subjects' dietary and exercise compliance, assess compliance with investigational products and collect all the investigational products.

Follow-up Phase – Period D (4 weeks; Visit 14)

All subjects completing period C or those who discontinue study medication during period C will be followed for an additional 4 weeks to assess safety parameters. Between weeks 12 and 16, the Investigator may add, at their discretion, any therapy that is clinically indicated to control the subject's hyperglycemia.

Table 1 Study Plan

Procedure	Screening	Wash-out Period (Period A) ^b		Placebo Lead-in Period (Period B)		Double-blind, Placebo-controlled, Treatment Period (Period C) ^c							Follow-up period (Period D)	
	Wk-12 ~ -10 ^a	Wk -10	Wk -6	Wk -4 Entry lead-in	Wk-1	Wk 0 Randomisation	Wk 1	Wk 2	Wk 4	Wk 6	Wk 8	Wk 10	Wk 12 End of Treatment	Wk 16
Visit	1	2	3	4 (-4w)	5 (-1w)	6	7	8	9	10	11	12	13	14
Informed Consent ^a	X													
Review In/Ex Criteria or Randomization Criteria	X					X								
Complete Medical History	X													
Complete Physical Examination	X			X		X							X	
Brief Physical Examination							X	X	X	X	X	X		X
Vital Signs, Body Weight	X			X		X	X	X	X	X	X	X	X	X
Orthostatic Blood Pressure, Heart rate						X		X	X				X	X
Height, Body Mass Index	X													
Waist Circumference	X					X							X	
ECG				X		X							X	
Concomitant medications	X	X	X	X	X	X	X	X	X	X	X	X	X	X
Dietary/exercise instruction/review		X	X	X	X	X	X	X	X	X	X	X	X	X
Contact Registration Centre	X ^e					X ^e							X ^e	
Dispense Glucose Meter and supplies/provide instructions ^d	X	X	X	X	X	X	X	X	X	X	X	X	X	
Adverse Events Assessment				X	X	X	X	X	X	X	X	X	X	X

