- c All randomized subjects not completing the treatment period should have Visit 13 procedures done as soon as possible but at the latest within 7 days after discontinuation of investigational products, and subsequently enter the 4-week follow-up period.
- d Glucose meter is provided to subjects and they check their blood glucose values if they have symptoms of hypoglycemia.
- e Call Registration Center to enroll subjects when informed consent is obtained at Visit 1, to randomize subjects at Visit 6, and when subject completes Period C or early discontinue Period C.
- f Subjects treated with anti-diabetic medication up to enrolment should have HbA1c ≤ 8% at Visit 1 to enter Period A, and the other type of subjects will enter Period B if HbA1c ≥ 7% but ≤ 10% at visit 1. All subjects should have HbA1c ≥ 7% but ≤ 10% at visit 5 to be randomized.
- g Subjects treated with anti-diabetic medication up to enrolment will be withdrawn if FPG > 240 mg/dL.
- h At Visit 6, OGTT is performed if FPG is <180 mg/dL at visit 5. At Visit 13, OGTT is not performed in subjects who did not perform OGTT at Visit 6, subjects who did not complete period C or subjects whose FPG is ≥ 180 mg/dL at Visit 12. At Visit 13, blood samples are drawn 60, 90, 120, 180 and 240 minutes after administration of 75 g oral glucose solution.
- i Plasma samples for analysis of dapagliflozin are obtained before administration of dapagliflozin at Visit 7, 10 and 12. At Visit 13 plasma samples are obtained at 60, 90, 120, 180 and 240 minutes after administration of dapagliflozin. If the subjects perform OGTT at Visit 13, plasma samples are obtained simultaneously with OGTT blood samples.
- j 24 hour urine collection is done in subjects who give consent. 24 hour urine is collected from the morning of the previous day to the visit up to the morning of the visit. 24 hour urine collection is allowed to be done on a separate day of the study visit if collected within 7 days before the visit. Subjects do not need to perform 24 hour urine collection at visit 6 if they do not meet HbA1c ≥ 7% but ≤ 10% at Visit 5. At Visit 13(Week 12), 24 hour urine is not performed in subjects who did not complete Period C

Clinical Study Protocol
Drug Substance Dapagliflozin
Study Code D1692C00005
Edition Number 1
Date

k Includes anti-HAV (IgM, IgG), HBsAg, and anti-HCV, and anti-HBc

Table 2 Visit design and time windows

Visit ID	Visit description	Visit window
Visit 1	Enrolment (Screening) ^a	-12 weeks

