Visit 2	Entry of washout ^b	-10 weeks ±3 days
Visit 3	Washout period ^b	-6 weeks ±3 days
Visit 4	Entry placebo lead-in	-4 weeks ±3 days
Visit 5	Placebo Lead-in Period	-1 week ±3 days
Visit 6	Randomisation/Start of treatment	±0 days
Visit 7	Treatment Period	1 week ±3 days after Visit 6
Visit 8	Treatment Period	2 weeks±3 days after Visit 6
Visit 9	Treatment Period	4 weeks ±3 days after Visit 6
Visit 10	Treatment Period	6 weeks ±3 days after Visit 6
Visit 11	Treatment Period	8 weeks ±3 days after Visit 6
Visit 12	Treatment Period	10 weeks ±3 days after Visit 6
Visit 13	Treatment Period/End of treatment	12 weeks ±3 days after Visit 6
Visit 14	Follow-up Period	16 weeks ±3 days after Visit 6

a If the results of central laboratory tests are available by Visit 2 (Week -10), Visit 1 can be done between 10 to 12 weeks before Visit 6.

b Strictly treatment naïve subjects at enrolment, Relatively treatment naïve subjects at enrolment, or subjects treated with anti-diabetic medication prior to enrolment can skip Visit 2 and Visit 3. If the results of central laboratory tests are available by Visit 4 (Week -4), Visit 1 can be done between 4 to 6 weeks before Visit 6.

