3.2 Rationale for study design, doses and control groups

This study is a randomized, double-blind, placebo-controlled study to assess the efficacy and safety of dapagliflozin in Japanese subjects with T2DM who have inadequate glycemic control. This study is also designed to be as similar as possible to the global phase 2b study (MB102008) in order to enable comparison of the efficacy and safety results between the two studies.

Placebo lead-in period is set to remove any bias regarding placebo effect. Patients receiving prior therapy will complete a 6-week washout period, and 4 weeks of placebo lead-in for a total washout period of 10 weeks to eliminate effects of the prior therapy. The reason for 10 weeks of washout is as follows:

- (a) Adequate washout of all prior oral anti-diabetic agents and their pharmacodynamic effects including the ones that have prolonged effects such as Pioglitazone
- (b) Stabilization of HbA1c after discontinuation of any oral anti-diabetic agents takes 8-12 weeks. 10 weeks of washout allows for an adequate stabilization of HbA1c after washout of oral anti-diabetic agents prior to randomization of patients to dapagliflozin versus placebo treatment arms in this study.

The Follow-up period is set to examine the reversibility of potential adverse events after taking the last dose.

Doses of dapagliflozin and control groups

Placebo-controlled study is essential to evaluate the blood glucose-lowering effects of dapagliflozin.

In this study, dapagliflozin doses 1 mg, 2.5 mg, 5 mg and 10 mg were chosen based on efficacy, pharmacodynamic and safety data from the global phase 1 and 2 studies, and the Japan phase 1 studies. This dose range is supported by the following reasons:

- In the global phase 1 and 2a studies, maximal glucosuria was seen at the 10 to 20 mg dose level. Doses ≥ 20 mg only increased the duration of glucosuria. In the global phase 2b study (MB102008), glucosuria appeared related to dose, with maximal glucosuria seen at the 20 and 50 mg doses.
- In the global phase 2b study (MB102008), dapagliflozin improved glycaemic parameters throughout the dose range of 2.5 mg to 50 mg daily, with most of the efficacy realized within the dose range of 2.5 mg to 10 mg. There was no apparent dose relationship beyond 10 mg for HbA1c, though there was evidence for a continued dose-response relationship up to 50 mg with respect to FPG change.

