For subjects who are discontinued from the study as a result of sustained elevated liver safety abnormalities as described above, study medication will be discontinued, the Sponsor notified and the early termination (End-of-Treatment) visit performed within 3 days of the confirmed laboratory results. Additional blood sampling must be done within 3 days of the confirmed laboratory results in conjunction with an early termination (End-of-Treatment) visit, in addition to the procedures noted above. A “Liver Discontinuation” visit laboratory kit, in addition to the Specialized Liver Panel kit as noted below, will need to be used to collect recommended blood samples. Additionally, supplemental (unscheduled) visit eCRF pages as well as supplemental eCRFs will need to be completed to collect “Liver Discontinuation” information. Patient should also be scheduled for a Follow-up visit (i.e. procedures of Visit 14) 4 weeks after discontinuation of investigational product. A referral consultation to a hepatologist or gastroenterologist (specializing in liver abnormalities) should be obtained. Any additional tests and/or examinations should be carried out at the discretion of the Investigator. Any further investigations and laboratory results for subjects with abnormal laboratory values at the safety follow-up visit should be made available to the Sponsor upon request.

Following the Early Termination (End-of-Treatment) visit, the Investigator should continue to monitor the subject’s liver tests every 3 days following receipt of the prior laboratory results until the ALT and AST are $\leq 2X$ ULN or until ALT and AST are at or below baseline levels. The frequency of retesting can decrease to once a week or less if abnormalities stabilize and the subject is asymptomatic.

Specialized Liver Panel

For **all** subjects who are being monitored frequently as a result of confirmed AST and/or ALT > 3X ULN, additional central laboratory tests will be performed within 3 days of receipt of confirmatory results. These laboratory tests will study the possible causes of the increased ALT and/or AST and/or TB, and may include, but are not limited to, the following tests:

- Hepatitis A IgM
- Hepatitis BsAg
- Hepatitis B Core Ab IgM
- Hepatitis C virus RNA
- Hepatitis C Ab
- Hepatitis E IgM
- Epstein-Barr Virus (EBV) IgM Ab
- Lactate Dehydrogenase (LDH)
- Gamma-glutamyl-transpeptidase (GGT)
- Carbohydrate deficient transferrin (CDT)
- Prothrombin time (PT/INR)

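### For subjects who stop study drug early, the protocol times Visit 14 inconsistently: at Week 16 from randomisation, or at the end of a 4-week follow-up

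*Protocol*

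**What the plan says.** Two sets of statements in the protocol bear on when an early stopper has Visit 14, the only scheduled follow-up visit.

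**Week 16 from randomisation.** Section 6.2.5 names two groups for follow-up: (a) those who complete Period C and (b) those who stop double-blind drug before Week 12. For both it says "Visit during this phase is scheduled to occur at Week 16". Table 2 gives the Visit 14 window as "16 weeks ±3 days after Visit 6", and its footnotes make exceptions only for screening and wash-out visits. The Period C text in Section 3.1 adds "Once a patient is randomised, all visits should be scheduled relative to Visit 6".

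**A 4-week follow-up.** The Period D text in Section 3.1 says that "those who discontinue study medication during period C will be followed for an additional 4 weeks to assess safety parameters". Table 1 note c has non-completers undergo the Visit 13 procedures within 7 days of stopping "and subsequently enter the 4-week follow-up period". Section 5.8.2 likewise puts every randomised subject into a 4-week Period D. Section 6.2.5(b) itself starts Period D after the last dose. Amendment 1, Change 3 (the revised Appendix I text, which is in force) schedules the Visit 14 procedures "4 weeks after discontinuation of investigational product", for subjects discontinued because of liver abnormalities.

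Section 3.2 gives the purpose: "The Follow-up period is set to examine the reversibility of potential adverse events after taking the last dose". Section 6.4.3 has adverse events recorded through Period D.

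**The concern.** For a completer the two timings coincide. For an early stopper they do not, and Section 6.2.5 contains both: Period D starts at the last dose, yet its visit is at Week 16. For a Week 4 stop that makes Period D about 12 weeks long, not 4.

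The stake is the safety follow-up of early stoppers. If Period D exists to see whether adverse events reverse off drug, the interval between last dose and visit should be the same across subjects and sites. The timing a site adopts also sets how long adverse events go on being recorded. Liver stops have a fixed date; stops for creatinine, sodium, creatine kinase, haemoglobin or lack of glycaemic control do not.

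The rescue-therapy sentence in Section 3.1 has the same weakness. It allows added glucose-lowering therapy in study weeks 12 to 16, which does not fit someone who stopped for hyperglycaemia at Week 4.

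**Working it through.** No power or alpha figure is involved. The check is calendar arithmetic on the stated timings.

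**Inputs**
- Visit 14 at 16 weeks = 112 days after Visit 6, ±3 days (Table 2; Week 16 in 6.2.5).
- Follow-up of 4 weeks = 28 days (3.1 Period D; 5.8.2; Table 1 note c; amended Appendix I for liver stops).
- End-of-treatment (Visit 13) procedures at most 7 days after stopping (3.1; 5.8.2; Table 1 note c).
- Illustrative stops at Weeks 4, 6, 8 and 10, the visits with glycaemic discontinuation limits in Table 6. Real stop dates may fall a few days later because a repeat measurement is required.

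**Formulas**, with last dose on day *d* after Visit 6
- Week 16 reading: Visit 14 on day 112; time off drug = 112 − *d*.
- 4-week reading: Visit 14 on day *d* + 28 if counted from the last dose, and up to *d* + 35 if counted from an end-of-treatment visit 7 days later; time off drug = 28 to 35 days.
- Gap between readings = (112 − *d* − 35) to (112 − *d* − 28), that is 77 − *d* to 84 − *d*.

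| Stop | *d* | Visit 14, 4-week reading | Visit 14, Week 16 reading | Gap (days) | Days off drug: 4-week vs Week 16 reading |
|---|---|---|---|---|---|
| Week 4 | 28 | 56–63 | 112 | 49–56 | 28–35 vs 84 (81–87) |
| Week 6 | 42 | 70–77 | 112 | 35–42 | 28–35 vs 70 (67–73) |
| Week 8 | 56 | 84–91 | 112 | 21–28 | 28–35 vs 56 (53–59) |
| Week 10 | 70 | 98–105 | 112 | 7–14 | 28–35 vs 42 (39–45) |
| Completer | 84 | 112 | 112 | 0 | 28 vs 28 |

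Ranges in parentheses apply the ±3-day window of Table 2. The completer row takes Visit 13 on the day of the last dose.

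**Side check on carry-forward.** Table 7 schedules HbA1c and FPG at Visit 14. Counted from the last dose, Visit 14 precedes Week 12 when *d* + 28 < 84, that is when *d* < 56 (a last dose before Week 8). Under the Week 16 reading it never does.

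**The case against.** The best defence is that week numbers serve as visit names for early stoppers. The protocol has them do the Visit 13 (Week 12) procedures within 7 days of stopping, so Week 12 cannot mean day 84 there, and Week 16 in 6.2.5 may likewise just name Visit 14. Table 2 has no early-stopper exception for Visit 13 either, yet Visit 13 plainly moves. The 3.1 sentence on scheduling from Visit 6 sits in the Period C text beside the instruction not to let slippage accumulate, so it is mainly about visit drift. Every description of Period D points to 4 weeks.

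Much of this stands: the 4-week reading is the more likely intent. It does not close the gap. The Visit 13 exception is written out in three places; Visit 14 has one only for liver stops, and 6.2.5 puts early stoppers directly under the Week 16 sentence.

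Three stronger readings are tempting and are not supported.
- A reader might infer that 3.1, 5.8.2 and Table 1 note c each set Visit 14 at 4 weeks after stopping. They give a length; only amended Appendix I names discontinuation as the anchor.
- A reader might infer that safety follow-up is lost. Section 6.4.3 has unresolved events followed for as long as medically indicated, and the sponsor may ask for more information. That follow-up is not entered in the eCRF, so the reassurance is partial.
- A reader might infer a bias in HbA1c or FPG through carry-forward of off-drug Visit 14 values. Section 12.2.1 read literally could pick up such a value for a last dose before Week 8, but whether off-treatment values are eligible is a rule commonly set in the SAP, which is not at hand. No error in the planned primary analysis is shown.

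**Conclusion.** The point holds as a wording inconsistency with a small, confined effect. Apart from liver stops, the protocol gives an early stopper two possible dates for Visit 14. They differ by 7 to 8 weeks for a Week 4 stop and by 1 to 2 weeks for a Week 10 stop, shrinking to nothing for completers. The spread within each range comes from the unstated start of the 4 weeks (last dose or end-of-treatment visit).

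What is affected is the off-drug interval of the reversibility check and the duration of adverse event recording in early stoppers, data that Section 12.2.2 summarises descriptively. Sample size and the primary analysis as planned are not affected. The documents give no expected number of early stoppers, so the number of subjects affected cannot be stated; the 4% in Section 12.3 concerns exclusion from the full analysis set and is not a discontinuation rate. The day counts assume nominal visit dates.

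**What to change.** - **Table 2 and Section 6.2.5:** add that, for subjects who stop early, Visit 14 is 4 weeks ±3 days after the last dose of investigational product. This extends to all early stoppers the anchor that amended Appendix I uses for liver stops, and gives each of them 25 to 31 days off drug (28 ± 3).
- **Table 1 note c:** say that the 4 weeks run from the last dose.
- **Section 3.1, Period D:** let the rescue-therapy sentence apply during Period D, after the Visit 13 procedures, in place of study weeks 12 to 16.
- **Optional, and may sit in the SAP:** state that Period D (Visit 14) values are not carried forward to Week 12. This is worth having once the 4-week rule is explicit, since Visit 14 then precedes Week 12 for last doses before Week 8.

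The cost is wording in four places in the protocol, plus the optional line. No visits, samples or subjects are added.
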